1 INTRODUCTION

Small changes in lens design, the process of fabricating contact lenses, and changes to packaging solutions can have an impact on their on-eye performance and comfort. CooperVision is evaluating the clinical performance of an investigational silicone-hydrogel lens called Invigor I (test) when worn on a daily disposable wear modality over 1 week (for each lens) in a randomized, bilateral, cross-over, dispensing study. [REDACTED]

[REDACTED] The study lenses are specifically designed to be a daily disposable wear silicone hydrogel contact lens, replaceable after each use.

2 STUDY OBJECTIVE

The purpose of this study is to investigate the overall clinical performance of the Invigor IA (test) daily disposable silicone hydrogel lens compared to the Invigor IB (control) lens that is identical to the marketed lens Select 1 Day, and is labelled with an investigational label for the purpose of this study.

This is a study to validate the performance of Invigor 1 (test) lenses when worn on a daily disposable wear modality over 1 week (for each lens).

The primary variables of interest are:

- Comfort and preference (subjective ratings)
- Vision (logMAR, and subjective ratings)
- Anterior ocular health (corneal staining and conjunctival staining, etc.)
- Discontinuation rate

[REDACTED]

[REDACTED]

[REDACTED]

[REDACTED]

[REDACTED]

[REDACTED]

[REDACTED]

2.1 STUDY HYPOTHESIS

The study hypothesis is that the Invigor IA lens (test) will perform as well as or better than the Invigor IB (control lens) in terms of the primary outcome variables evaluated.

Further, that there will be no contraindications to continued lens wear with the Invigor IA (test) lens when worn on a daily disposable basis.

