7.5.3 VISIT 3: ASSESSMENT OF PAIR # 2 AND STUDY EXIT

This visit will occur 6-10 days after dispense of lens pair #2.

Procedures for assessment of pair # 2 will be followed (similar to assessment of pair # 1) as detailed in the follow up visit section 7.5.2.

- Participant will also rate their overall preference between lens pair #1, lens pair-#2 or no preference (and reason for preference) for a number of considerations that include:
 - Overall comfort preference, and reason for preference.
 - Overall vision preference, and reason for preference.

- The lenses will be removed by the participant and retained in the CCLR (see section 7.4.6 for disposing consumables).
- Slit lamp biomicroscopy assessment will be conducted according to the CVI approved study biomicroscopy CRF, using sodium fluorescein dye.
- Exit visual acuity will be performed with habitual glasses.
- The participant will be discharged and will sign the study completion forms.

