11.3 STATISTICAL ANALYSIS

All data will be analyzed by the CCLR at the University of Waterloo. Summary statistics will be produced (e.g. mean, standard deviation). Data analysis will be conducted using Statistica, SPSS or SAS. Descriptive statistics will be provided on information regarding baseline variables (age, gender, refractive error distribution, etc.), and follow up visits (e.g. mean, SD). Analysis of variables will be conducted separately on each eye, and data will not be pooled. For assessments conducted for each eye separately, the right eye will be used for analysis if there is no difference between eyes. If a general difference is found (e.g. for paired t-test / Wilcoxon matched pairs) between OD and OS, a comment will be provided.

A Binomial test will be used to analyze the results for the count data of subjective preferences. The number of “no preference” will be evenly distributed to the two options on the basis they would be equally likely to choose either.

[REDACTED]	[REDACTED]	[REDACTED]

The critical alpha level for statistical significance will be set at $p \leq 0.05$, with no adjustments for multiple comparisons.

All participants who were evaluated will be used in the analysis. In the event of missing data, individual data points may be excluded in the analysis and not extrapolated from the collected data.

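### Preference is a primary variable under an 'as well as or better' hypothesis, but its readable analysis, a Binomial test after splitting the undecided evenly, can support 'better' and not 'as well as'

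*Combined protocol and SAP*

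**What the plan says.** Section 2 names "Comfort and preference (subjective ratings") first among the primary variables of interest. Section 2.1 states the hypothesis that the test lens "will perform as well as or better than the Invigor IB (control lens) in terms of the primary outcome variables evaluated".

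Preference is collected once, at Visit 3 (Section 7.5.3): "Participant will also rate their overall preference between lens pair #1, lens pair-#2 or no preference". The items named there are "Overall comfort preference, and reason for preference" and "Overall vision preference, and reason for preference". Each response therefore has three categories.

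Section 11.3 gives the analysis: "A Binomial test will be used to analyze the results for the count data of subjective preferences". The undecided answers "will be evenly distributed to the two options on the basis they would be equally likely to choose either". Significance is set at p ≤ 0.05 with no multiplicity adjustment. On summaries it says "Summary statistics will be produced (e.g. mean, standard deviation"), as examples. Section 11.1 targets about 30 completers from about 40 dispensed.

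The readable text does not give the null proportion, the sidedness, an interval for a preference proportion, a rule for an odd number of undecided answers, or a rule linking the test result to the hypothesis. Parts of Sections 2, 11.1 and 11.3 are redacted, and no Section 11.2 is visible.

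**The concern.** The hypothesis has two halves. Rejecting a 50:50 null in favour of the test lens would support 'better'. Nothing in the readable analysis addresses 'as well as', because failing to reject is not evidence of similarity. With about 30 completers, a non-significant result is compatible with a clear majority preferring control.

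The tie rule adds a second problem. Sharing undecided answers equally treats people who made no choice as if they had chosen. It pulls the observed share towards one half while keeping 30 as the denominator, so the test becomes conservative as ties grow. Under an 'as well as' hypothesis, that makes a real preference for control harder to see. Unless the three counts are shown, a reader cannot separate true similarity from an uninformative result.

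**Working it through.** **Inputs.** Completers n = 30 (Section 11.1) and alpha 0.05 (Section 11.3). A 50:50 null is assumed. The test is taken as two-sided, with other readings shown. The true preference shares and the undecided counts are illustrations, because the readable text gives none. The plan has no readable power or margin figure to reproduce.

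**1. Rejection region, nobody undecided.** Let X be the number preferring control, X ~ Bin(30, 0.5) under the null, with p = 2·P(X ≥ k).
- k = 20: 2 × 0.0494 = 0.099, not significant. The exact 95% CI for 20/30 is 47% to 83%.
- k = 21: p = 0.043, significant.

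So any count from 10 to 20 of 30 is non-significant.

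**2. Chance of a non-significant result when control is truly preferred**, P(10 ≤ X ≤ 20), with other readings beside it:

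| Reading | 60% | 65% | 70% |
|---|---|---|---|
| Two-sided, n = 30 | 82% | 64% | 41% |
| One-sided towards control, n = 30 (20 needed) | 71% | 49% | 27% |
| Two-sided, n = 40 (27 needed) | 79% | 56% | 30% |

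If the test is one-sided towards the test lens, every control majority is non-significant.

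**3. Even number undecided.** With u undecided, X ~ Bin(30 − u, π). The planned rule tests X + u/2 out of 30; dropping ties tests X out of 30 − u.
- u = 2, 4, 6 or 8: the two-sided decisions are identical (for u = 6, both leave 7 to 17 of 24 non-significant).
- u = 10: the split leaves 5 to 15 of 20 non-significant, and dropping leaves 6 to 14. The true size is 1.2% against 4.1%. Non-significance at 60/65/70% is 95/88/76% against 87/75/58%.
- Example, 15 control, 5 test, 10 undecided. Split: 15 + 5 = 20 of 30, p = 0.099. Among choosers: 15 of 20 = 75% (CI 51% to 91%), p = 0.041.

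**4. Odd number undecided.** The answers cannot be shared equally, so the result depends on who receives the odd one.
- 18 control, 7 test, 5 undecided. Control receives 2: 20 of 30, p = 0.099. Control receives 3: 21 of 30, p = 0.043. Ties dropped: 18 of 25, p = 0.043.
- 20 control, 9 test, 1 undecided. Odd answer to control: 21 of 30, p = 0.043. Odd answer to test: 20 of 30, p = 0.099. Dropped: 20 of 29, p = 0.061.

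So the decision can turn on an unstated convention with as few as one undecided answer. In the second example the split can also be less conservative than dropping.

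**5. Which interval shows similarity.** Take 3 test, 3 control, 24 undecided. The exact CI among choosers (3 of 6) is 12% to 88%, which looks uninformative although 24 of 30 saw no difference. The net preference is d = (test − control)/n, with SE = √[((test + control)/n − d²)/n]. Here d = 0 and SE = √[(6/30)/30] = 0.082, so the approximate 95% CI is −16 to +16 points. For the example in step 3, d = (5 − 15)/30 = −33 points and SE = √[(20/30 − 0.111)/30] = 0.136, giving a CI of −60 to −7 points. The net preference is informative in both cases.

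**The case against.** The strongest reply is that no sentence in the plan is wrong. It never says that p > 0.05 will be read as support for 'as well as'. Redaction falls where a margin or interval rule would sit: after the primary variables, after the sample size and directly after the preference paragraph. Mean and SD are given only as examples, so the absence of a visible interval is weak evidence. All of this stands. A reader might infer that the sponsor plans to claim equivalence from a non-significant test, or that the plan has no margin. The documents support neither inference.

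A second reply is that the tie rule is stated openly and often changes nothing. That is true for even undecided counts up to 8 of 30, two-sided. It would be too generous to conclude that the split matters only when ties are many, because the odd-count examples show otherwise.

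A third reply is that an interval alone does not prove similarity. That is also correct: a formal conclusion needs a prespecified margin, and without one the statement can only be descriptive.

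What remains is the readable mismatch between hypothesis and test, the tie rule's effect, and the missing odd-count convention.

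**Conclusion.** The point holds as a minor one. As far as it can be read, the preference analysis can support 'better' but not 'as well as', and at 30 completers it would miss a true 60:40 preference for control about four times in five. The even split makes the test conservative when many are undecided, and with an odd count the decision can depend on an unwritten rule.

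This rests on a 50:50 null, on two-sided testing for the main figures, and on assumed undecided counts. The one-sided and n = 40 figures do not alter the conclusion. It concerns preference only; nothing is claimed about how the other primary variables are analysed. Redacted text may already hold a margin or interval rule, so the missing rule is a question for the sponsor and not a fault found.

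**What to change.** In Section 11.3, before unmasking, for the comfort and vision preferences:
- State the null proportion, the sidedness and how an odd undecided answer is assigned.
- Report the three counts: test, control, no preference.
- Keep the planned split result. Beside it, give the exact Binomial test and exact 95% CI among those who chose, and the net preference (test minus control over all respondents) with its 95% CI, so that many undecided answers count as evidence of similarity.
- Base any 'as well as' statement on the interval, against a margin if the sponsor has one and otherwise descriptively, and not on p > 0.05.
- Confirm whether redacted text already covers this.

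The cost is a few lines of analysis on the same data and sample size, with the planned test kept. The real downside is that 'as well as' becomes harder to claim. With no true difference and all 30 choosing, an exact lower limit above 30%, 35% or 40% for the test lens (illustrative limits, not from the documents) needs at least 15, 17 or 18 choices for it. That is reached 57%, 29% or 18% of the time. A descriptive estimate with its interval is therefore the realistic route at this size.

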3 STUDY DESIGN

This will be a, prospective, double-masked, randomized, bilateral, 1 week cross-over, dispensing study comparing the Invigor IA (test) lens against the Invigor IB (i.e. Select 1 Day) (control) lens. Each participant will be randomized to wear either the test or control as a matched pair first. Both test and control lenses will be used in a daily disposable lens wear modality for one (1) week. It is anticipated that this study will involve 3 scheduled visits:

- Visit 1: Enrollment/ Screening/ Baseline/Fitting/Dispensing of lens pair #1 (either test or control lens);
- Visit 2: 1-week follow-up visit for lens pair #1, and dispensing visit of lens pair #2 (either test or control lens) 6-10 days after lens pair #1 dispense;
- Visit 3: 1-week follow-up visit for lens pair #2 (6-10 days after lens pair #2 dispense) and exit.

The study design is shown in Figure 1.

[figure not shown]

Figure 1: Study design

Each participant will be randomized to wear either the test or control as a matched pair first. Both test and control lenses will be used in a daily disposable lens wear modality.

4 ETHICS REVIEW / STATEMENT OF COMPLIANCE

4.1 RELEVANT STANDARDS / GUIDELINES

This protocol document has been developed in accordance with the following:

- ISO 14155 Clinical Investigation of Medical Devices for Human Subjects
- ICH Harmonized Tripartite Guideline for Good Clinical Practice
- The University of Waterloo's Guidelines for Research with Human Participants
- Tri-Council Policy Statement: Ethical Conduct for Research Involving Humans, 2nd Edition
- Declaration of Helsinki

4.2 INSTITUTIONAL REVIEW BOARD

This study will be conducted in accordance with Institutional Review Board regulations (U.S. 21CFR Part 56.103) or applicable IEC regulations. Copies of all IRB/IEC correspondence with the investigator/sponsor will be kept on file.

This protocol will be submitted to and reviewed through the Office of Research Ethics (ORE) at the University of Waterloo.

The conduct of this study has been approved at the Institutional Review Board at University of Waterloo, Canada, through ORE file number 21616.

4.3 INFORMED CONSENT

Informed consent shall be obtained in writing from the participant prior to their enrollment in the study, and before any procedure specific to the clinical investigation is carried out.

5 CLINICAL TRIAL REGISTRATION

This study will be registered in the clinical trials registry (www.ClinicalTrials.gov) by the study sponsor.

6 POTENTIAL RISKS AND BENEFITS TO HUMAN PARTICIPANTS

This is a minimal risk study. The investigational contact lenses used in this study are intended for daily wear (not extended wear) with usage consistent with typical daily wear.

This study is considered to be a non-significant risk study based on United State Food and Drug administration (FDA) and International Standards Organization (ISO) guidelines due to the daily wear nature of the study.

Further, the investigational lens will be tested for sterility and biocompatibility prior to release.

Complications that may occur during the wearing of contact lenses include discomfort, dryness, aching or itching eyes, excessive tearing, discharge, hyperemia and variable or blurred vision and infiltrates. More serious risks may include photophobia, iritis, corneal edema or eye infection.

Although contact lens-related infections are very infrequent, the possibility does exist. The incidence of infection due to day-wear soft lenses is 0.035%. Almost always an infection will occur only in one eye. This risk is assumed by 35-million Americans who currently wear contact lenses. The lenses being used may not have the exact prescription power needed by the participant (within +/-0.25 of their required contact lens powers). It is possible that some participants may experience minimal "eye strain" when focusing through this reduced/extra power which may cause headache.

Routine clinical procedures including auto-refraction, auto-keratometry, visual acuity, anterior ocular health assessment, and contact lens fitting will be used. In addition, high magnification imaging (including video and still images) of the lens fit may be made using 35 mm or digital cameras.

There might not be direct benefits to the participants in this study. However, participation in a study may contribute to scientific research information that may be used in the development of new contact lens products. In addition, participants will receive an examination of the front part of their eyes and may have the opportunity to try a different type of soft contact lenses at no cost to them.

7 MATERIALS AND METHODS

7.1 RANDOMIZATION

A randomization schedule will be generated. The final study randomization schedule will be generated by the Head of the CCLR Data Management Team, and provided to the research assistants for the study. Study investigators will remain masked to the randomization schedule until the study is completed and the database is locked.

7.2 Masking

Both participant and investigator will be masked as to lens type and lens assignment (control vs. test). The contact lens coding will be masked to both the investigators and participants as much as possible. A computer generated randomization scheme (sample randomization in Appendix 14) will be used and will be provided to an unmasked member of staff at the study site. Study investigators will remain masked to the randomization schedule until the study is completed and the database is locked. Lenses dispensed to participants may be over-labelled, however the safety information on the outer package label of the contact lens, shall be clearly visible.

Under normal circumstances, the investigator mask will not be broken until all subjects have completed the study and the database is finalized, the subject mask will not be broken until their involvement in the study is complete. Otherwise, the mask should be broken only if a specific emergency treatment or course of action would be dictated by knowing the treatment status of the subject. In the event the mask is broken, the sponsor must be informed as soon as possible. The date, time, and reason for the unmasking must be documented.

7.3 Participants

Up to 40 participants will be successfully enrolled and dispensed/randomized with the study products, with a target of 30 participants completing the study. Participants will be recruited using CCLR records and advertising approved by the UW Office of Research Ethics (Appendices 2 &11). Informed consent will be obtained for all participants prior to their enrolment in the study (Appendix 1).

Each participant will be given a unique ID number. Additionally, all participants must meet the study inclusion and none of the exclusion criteria listed below.

7.3.1 INCLUSION CRITERIA

A person is eligible for inclusion in the study if he/she:

- Is at least 17 years of age and has full legal capacity to volunteer;
- Has had a self-reported oculo-visual examination in the last two years;
- Has read, understood, and signed the information consent letter;
- Is willing and able to follow instructions and maintain the appointment schedule;
- Has a visual acuity of 20/30 or better (in each eye) with their habitual vision correction, or 20/20 best-corrected vision (for binocular distance acuity);
- Must be able to achieve 20/30 or better (in each eye) with the study lenses;
- Currently wears soft contact lenses for at least 3 days per week, 8 hours each day;
- Requires spectacle lens powers between -0.75 and -06.50 diopters sphere (0.25D steps);
- Has no more than 0.75 diopters of refractive astigmatism;
- Has clear corneas and no active* ocular disease;
- Has not worn lenses for at least 12 hours before the examination.

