7.3.2 EXCLUSION CRITERIA

A person will be excluded from the study if he/she:

- Is presently participating in any other clinical or research study including eye related clinical or research study;
- Has never worn contact lenses before.
- Has any systemic disease affecting ocular health.
- Has any active* ocular pathology or severe insufficiency of lacrimal secretion (moderate to severe dry eyes) that would affect the wearing of contact lenses.
- Is using any systemic or topical medications that will affect a study outcome variable, and/or ocular health.
- Has any known sensitivity to fluorescein dye or products to be used in the study.
- Has persistent, clinically significant corneal or conjunctival staining using sodium fluorescein dye.
- Has any clinically significant lid or conjunctival abnormalities, active neovascularization or any central corneal scars.
- Is aphakic.
- Has undergone corneal refractive surgery.
- Is pregnant, lactating, or planning a pregnancy at the time of enrolment (by verbal confirmation at the screening visit).

* For the purposes of this study, active ocular disease is defined as infection or inflammation which requires therapeutic treatment. Mild (i.e. not considered clinically relevant) lid abnormalities (blepharitis, meibomian gland dysfunction, papillae), corneal and conjunctival staining and dry eye are not considered active ocular disease. Neovascularization and corneal scars are the result of previous hypoxia, infection or inflammation and are therefore not active.

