7.3.3 REPEATED SCREENINGS

In some circumstances a repeated screening may need to be scheduled. Examples include, but are not limited to:

- a) Incomplete information available at time of screening to determine eligibility (e.g. current lens brands worn, history from current eye care practitioner etc.)
- b) Study procedures unable to be completed in time scheduled for visit;
- c) Study products not available at the time of the screening visit;
- d) A transient health condition which may affect the eye(s) (e.g. a common cold, active allergies, fatigue etc.)
- e) The short term use of medications (e.g. antibiotics, antihistamines etc.)

f) Reassessment of baseline ocular conditions (e.g. corneal and/or conjunctival staining, scars etc.)

The maximum total number of screenings permitted will be 3.

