7.4 STUDY MATERIALS

7.4.1 CONTACT LENS

Participants will be randomized to receive either the test or control lens as a matched pair at each visit per a predetermined randomization schedule (Appendix 14). The lenses (test and control) will be labelled as Invigor IA (test) and Invigor IB (control).

The Invigor IA (test) lens is an investigational product and will be subject to pre-clinical assessment before being released for the study. This lens is not commercially available in Canada and therefore an ITA (investigational testing authority) from Health Canada has been received.

The Invigor IB (control) i.e. Select 1 Day lens is approved by FDA and Health Canada, and is commercially available in Canada and the USA, however for the purpose of this study, it has been labelled as Invigor IB and is covered under an ITA issued by Health Canada.

Details of the Invigor IA (test) and Invigor IB (control) study lenses used in this study are shown in Table 1. The test lens is the Invigor IA (test) lens and approved by Health Canada for use in the study.

Table 1: Study lenses used in this study

	Invigor IA (test)	Invigor IB (control) (i.e. Select 1 Day)
Manufacturer	CooperVision	CooperVision
HC License No.	-	81009
Material	somofilcon A	somofilcon A
Health Canada license #	-	81009
EWC (%)	56%	56%
Dk/t (-3.00D)	86.0	86.0
BOZR (mm)	8.6	8.6
Diameter (mm)	14.0	14.0
Sphere power (D)	-1.00 to -6.00 (0.25 steps)	-1.00 to -6.00 (0.25 steps)

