7.5.1 VISIT 1: SCREENING / BASELINE VISIT / DISPENSING PAIR #1

Participant will be assigned a unique participant/Study ID number after signing the ICL. The investigator will determine participant eligibility using the inclusion and exclusion criteria. Ineligible participants will be discontinued from the study.

The following evaluations will be performed to assess eligibility according to the Inclusion and Exclusion Criteria at the screening and baseline visit:

- The patient is expected to attend the screening / baseline visit not wearing their habitual contact lens products.
- The participant will be required to read and sign an Informed Consent Form prior to enrolment. When the participant has signed the consent form, the participant will be considered to be enrolled in to the study.
- Participant demographics and medical history (age, sex, race and ethnicity, medical conditions, medications, allergies)
- Contact lens history (own lens information, and wear time)
- Baseline visual acuity with spectacles or spectacle refraction.
- Auto refraction/auto keratometry: Horizontal and Vertical K readings (D)
- Sphero-cylindrical refraction (D), and best sphere refraction (D) & monocular & binocular distance visual acuity (high contrast) (logMAR)
- Slit lamp biomicroscopy will be assessed according to the approved study biomicroscopy CRF (Appendix 4).

- The investigator will confirm that the patient meets the criteria set out in the inclusion criteria, and none of the exclusion criteria and is eligible to continue in the study.
- The participant will be assigned a randomization ID and the first pair of contact lenses (either test or control) will be selected according to the randomization table.
- Contact lens power and fit may be evaluated at the screening visit or at the baseline visit.

[REDACTED]

[REDACTED]

[REDACTED]

[REDACTED]

- The contact lenses will be dispensed by a research assistant / study coordinator / technician (in a manner which does not unmask the participant and investigator).
- The lenses will be inserted by the participant from the blister pack as described in Section 7.4.3 of the Protocol.
- The contact lenses will be fitted and allowed to settle (Appendix 3).
- Initial subjective ratings (Appendix 16) include:

- Initial comfort (0-100 scale) and comments

[REDACTED]

[REDACTED]

- Vision quality / clarity (0-100 scale) and comments

[REDACTED]

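### Habitual wearers of the control product (Select 1 Day) are not excluded and, in the readable text, not analysed separately; for any who enrol, comfort and preference compare a familiar lens with a new one

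*Combined protocol and SAP*

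**What the plan says.** **Entry.** The only criterion on habitual lenses in section 7.3.1 is "Currently wears soft contact lenses for at least 3 days per week, 8 hours each day". No brand is named. In section 7.3.2 the one exclusion tied to lens history is "Has never worn contact lenses before". Neither list shows a redaction.

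**Control lens.** Section 2 describes it as the "Invigor IB (control) lens that is identical to the marketed lens Select 1 Day", and section 7.4.1 adds that it "is commercially available in Canada and the USA". The study runs at a Canadian university site.

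**Comparison.** Comfort and preference stand first among the primary variables in section 2. Each lens is worn for 6 to 10 days, with a 10-minute break between pairs (section 7.5). The readable text describes no run-in.

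**Masking and lens parameters.** Section 7.2 says: "Both participant and investigator will be masked as to lens type and lens assignment (control vs. test". Table 1 gives both lenses the same material, water content, Dk/t, base curve, diameter and power range.

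**Habitual brand.** Visit 1 records "Contact lens history (own lens information, and wear time". Section 7.3.3 gives as one reason for a repeat screening "Incomplete information available at time of screening to determine eligibility (e.g. current lens brands worn". No listed criterion uses brand, and the readable parts of sections 7.1 and 11.3 give it no role in randomisation or analysis.

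**Analysis.** Section 11.3 tests preference counts with a binomial test at 0.05, divides answers of no preference equally between the two lenses, and analyses everyone who was evaluated. Parts of section 11 and of Visit 1 are redacted.

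**The concern.** A participant whose own lens is Select 1 Day has chosen the control, has kept wearing it and is adapted to it before the study starts. That person meets the test lens for the first time and has about a week with it. Any advantage from familiarity or self-selection belongs to the control lens whichever lens comes first. Randomised order balances period effects, so it does not cancel this one. Over-labelling hides the package but does not undo adaptation to a lens.

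Two primary variables are exposed, both subjective. The study hypothesis is that the test lens does at least as well as the control, so a pull toward control would count against the test lens for a reason unrelated to its performance. With about 30 completers, a handful of such participants can matter.

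**Working it through.** The documents give no figure to reproduce here: the sample-size rationale is redacted and the number of habitual Select 1 Day wearers is not stated. What follows is a sensitivity calculation.

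**Inputs from the documents**
- n = 30 completers (section 11.1).
- Binomial test at 0.05, with answers of no preference split evenly (section 11.3).

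**Assumptions**
- Two-sided test; the readable text does not say.
- k habitual control wearers among the 30, with k = 0, 3, 6 or 9.
- Each of them favours control with probability 0.8.
- Everyone else is at 0.5, or at 0.3 for control where the test lens is truly preferred 70:30.
- Either nobody or 30% answers no preference.

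**Critical count.** 2 × P(X ≥ 21 | 30, 0.5) = 0.0428, so the test rejects at 21 or more, or at 9 or fewer. With 20 the value is 0.099, which does not reject.

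**Expected share for control, lenses equal for everyone else.** (0.8k + 0.5(30 − k))/30 = 0.50 + 0.01k, which is 50%, 53%, 56% and 59%.

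**All state a preference.** The count for control is Binomial(k, 0.8) + Binomial(30 − k, 0.5), convolved.

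**30% state none.** Each participant adds 1 for control with probability 0.7p, one half with probability 0.3, and 0 with probability 0.7(1 − p), where p is that person's chance of favouring control. Half counts are kept.

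*Chance of 21 or more for control, others 50:50*

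| Habitual control wearers | All state a preference | 30% none, split evenly |
|---|---|---|
| 0 | 2.1% | 0.6% |
| 3 | 4.2% | 1.1% |
| 6 | 7.9% | 2.1% |
| 9 | 13.9% | 3.9% |

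*Chance of showing the test lens better (9 or fewer for control), others 70:30 for test*

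| Habitual control wearers | All state a preference | 30% none, split evenly |
|---|---|---|
| 0 | 59% | 24% |
| 3 | 35% | 11% |
| 6 | 15% | 4% |

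**Sensitivity to the 80%.** With 70% to 90% and everyone stating a preference, the chance of a result for control is 3.4% to 5.1% (k = 3), 5.4% to 11.2% (k = 6) and about 8% to 22% (k = 9).

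**Comfort.** If such wearers score the control b points higher through habit, the mean difference shifts by b × k/30. For an assumed b = 5 on the 0–100 scale, that is 0.5, 1.0 and 1.5 points at k = 3, 6 and 9.

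**The case against.** The strongest reply is that the mechanism may be weak. The trial is double-masked and over-labelling is provided for. Table 1 shows two lenses alike in every listed parameter, so it is speculative that a wearer would recognise the control on the eye, or be adapted to one lens and not the other. This stands as a reason to expect a smaller effect. It does not exclude one: Table 1 is not a full description, and the protocol's introduction says that small changes in design, fabrication or packaging solution can alter comfort.

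The 80% figure and the direction also have no support in the documents. Someone who volunteers may be dissatisfied with their present lens. This stands too, and both are treated as assumptions.

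The even split of no-preference answers pulls the count toward 50:50. At 30% no preference, the chance of a significant result for control is a little over a quarter of what it is when everyone states a preference. That stands for the absolute risk. The relative rise from 0 to 9 wearers is similar either way (13.9/2.1 and 3.9/0.6, each about 6.5), and the loss of power remains.

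A reader might take the brand example in section 7.3.3 as proof that a criterion was dropped. The documents do not support that: it is one item in a list of examples, and brand may serve only to confirm that the habitual lens is soft.

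Finally, admitting soft-lens wearers of any brand is a legitimate choice of a broad population. It is compatible with reporting this one group separately.

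**Conclusion.** The gap is real but conditional. Current Select 1 Day wearers meet the entry criteria, nothing in the readable text separates them in the analysis, and randomised order does not remove an effect tied to the control lens.

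A reader might infer that the whole comfort and preference comparison sets a long-worn lens against a new one. It does so only for participants whose own lens is Select 1 Day. For everyone else both study lenses are new, unless they have worn the control in the past. Nor can one say that the plan ignores habitual lens altogether, because parts of section 11 and of Visit 1 are redacted.

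The size depends on assumptions: how many such wearers enrol, how strongly they lean, and how many participants state no preference. Across the main scenarios (80% leaning, 0 to 9 wearers), the chance of a significant preference for control when the lenses are otherwise equal runs from 2.1% to 13.9% if everyone chooses, and from about 0.6% to 3.9% with 30% undecided. With 6 such wearers, the chance of showing a true 70:30 advantage for the test lens falls from 59% to 15%, or from 24% to 4%. With none there is no effect. This is a worthwhile, inexpensive improvement and not a flaw that invalidates the trial.

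**What to change.** **Preferred.** Add to section 7.3.2 an exclusion for current habitual wearers of Select 1 Day. This would also give the brand information mentioned in section 7.3.3 a use. The cost is one eligibility line and a slightly smaller recruitment pool; the target of about 40 dispensed and 30 completing need not change.

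**If entry is not restricted.** Pre-specify in section 11.3, before unmasking, a sensitivity tabulation of comfort and preference without habitual Select 1 Day wearers, identified from the own-lens field at Visit 1. The cost is one extra table from data already collected.

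Judge that tabulation by the size and direction of the estimates, not by whether significance is kept, because fewer participants alone can lose it. For example, 21 of 30 (70%) gives a two-sided p of 0.043, while 17 of 24 (71%) gives 2 × 536,155/16,777,216 = 0.064.
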